We propose a single blinded, randomised prospective trial to risk profile our AF patients according to their non-invasive assessment of peripheral or central blood pressure including aortic stiffness estimate. The impact of central blood pressure, on the atrial electrophysiological substrate and clinical outcomes will be analysed. In addition, the relationship between central high blood pressure and non-invasive indicators of end organ (cardiac, vascular, renal and retinal) injury will be explored.

Specific Aims

The specific aims of the project are:

- 1. To determine the prevalence of central high blood pressure and aortic stiffness amongst AF patients referred to Centre for Heart Rhythm Disorders (CHRD), University of Adelaide.
- 2. Prognostic impact of central high BP treatment to pre-defined targets as per age (Table-1) on clinical outcomes in AF patients categorised as pre-HTN or HTN during brachial blood pressure assessment with or without HTN induced end organ insult.
- 3. To assess the correlation between indices of central high blood pressure and endorgan damage including structural as well as electrophysiological changes of left atrium, LV diastolic dysfunction including LVH and HTN nephropathy.
- 4. To assess the role of central blood pressure indices including central blood pressure response to exercise and posture in risk profiling of arrhythmia patients over and above conventional brachial BP.
- 5. Defining AF as an index of end organ insult secondary to HTN.

B. BACKGROUND AND PRELIMINARY STUDIES:

Introduction

HTN poses a major risk in development of AF and premature cardiovascular events [1, 2, 3{Schnabel, 2009 #926, 11, 12]. However, definition of HTN is a moving target and "optimal" treatment goals are still not clear. Besides epidemiological studies advocate BP control of \leq 120/80 mmHg from vascular risk standpoint, no strong outcome benefits of achieving such BP goals were reported by primary prevention studies in patients with

HIGH IMPACT AF Study Protocol Version 3.1, November 2017

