PAF patients, fulfilling the inclusion criteria will be recruited from Centre for Heart Rhythm Disorders (CHRD), Royal Adelaide Hospital (RAH), University of Adelaide and Cardiovascular Centre, Norwood (Professor [name]'s rooms). The participants (125 in each arm), will be randomized to intervention or control arm during the recruitment phase over a study period of 24 months. Participants will be risk profiled according to their age (30-50, 50-70, > 70 yrs.) and baseline central blood pressure (pre-HTN, HTN with or without end organ insult) into three groups. The control group will have conventional risk stratification as per brachial BP.

The following inclusion and exclusion criteria will be applied:

Inclusion Criteria

- 1. Age 20-80 years
- 2. Persistent and Paroxysmal AF patients
- 3. Able and willing to provide written informed consent

Protocol for HIGH IMPACT- AF study

Centre For Heart Rhythm Disorders, Royal Adelaide Hospital, University of Adelaide

Exclusion Criteria

- 1. Age <20years
- 2. Contraindications to exercise stress test (EST)
- 3. Pregnancy
- 4. Active malignancy or severe illness
- 5. Active Inflammatory disorder
- 6. Severe Aortopathy
- 7. Advanced valvular heart disease including aortic insufficiency (AI)
- 8. Constrictive or restrictive cardiomyopathy
- 9. Contraindications to non-contrast CMR (*only in selected patients scheduled for* *PVI*)

Withdrawal Criteria

Participants may withdraw at any time from the study. Patient will be excluded from the study if she will become pregnant during follow up.

D. STUDY DESIGN, TIME LINE AND INTERVENTIONS

It is a single centre, single blinded, prospective, randomised control study to collect and compare data to risk stratify our AF patients according to their aortic stiffness severity and central or peripheral blood pressure. Participants will be randomised to intervention or control group.

Intervention group will have their anti-hypertensive therapy titrated as per central blood pressure targets (Table-1), while the control group will have their brachial blood pressure treated as per current treatment guidelines (BP \leq 140/90 mmHg if risk of CVD is \leq 1% per year or 130/80mmHg if CVD risk is \geq 2% per year [21].

In addition, participants will be categorised according to their age (20-50yrs, 50-70yrs and >70yrs) and blood pressure into pre-HTN or HTN with or without end organ damage.

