Off note that the reported "normal range" of central blood pressure is estimated invasively while the participants are monitored in a controlled environment and under the effect of mild sedation. To prevent any harm to our study participants, we will take a holistic approach to risk stratify our patients while instigating treatment based on central or brachial pressures in order to avoid symptomatic hypotension along with drug side effects. The risk profiling will include age of the participants, aortic pulse wave velocity, baseline BP, degree of HTN induced end organ injury, BP response to exercise and central or brachial pressure indices including pulse pressure.

In case if patient has presenting BP characterised as grade II or higher HTN, a graduated approach will be adapted to lower the BP gradually by keeping an eye on the side effects of anti-HTN treatment.

CASP normal range						
Age (years)	Average (mmHg)	Minimum (mmHg)	Maximum (mmHg)			
20-30	101	90	112			
30-40	105	94	116			
40-50	108	97	119			
50-60	112	101	123			
60-70	115	104	126			
70-80	119	108	130			
80-90	122	111	133			

Table-1. Central Arterial Systolic Pressure (CASP) normal range as per age.

All AF patients will be assessed at baseline visits and at clinical follow-ups at RAH and Cardiovascular Centre, Norwood (Prof. [name]' rooms). Follow-up visits will be performed 3 monthly for the intervention group and six monthly for control as per treating electrophysiologist for 18-20 months (Tables 2 and 3). Participants will be risk stratified as per their central or brachial blood pressure indices into interventional and control group respectively.

The study will be approved by the ethics committee of RAH, University of Adelaide. Central blood pressure indices and carotid-femoral PWV analysis will be performed as per IMPULSE-AF validation study protocol. (CALHN Ethics and Research Committee Approval: R2010712, HREC Reference: HREC/16/RAH/269).

Table-2. Follow up and Investigations time line for Intervention Group (AFSS= AF symptom scale, CBP= central blood pressure, CPI= central pressure indices, EST= exercise stress test, PWV= pulse wave velocity, RFTs= Renal function test)								
0 months	3 months	6months	9months	12 months	15months	18-20 months		

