Exercise tolerance assessment as a part of AF management will be determined by Bruce protocol with gradual increase in treadmill gradient and velocity every 3 mins to achieve maximal target heart rate as per age by the following formula [220-Age for males, 220-Age x0.8 for females]. Where necessary, the test will be tailored as per individual age and effort tolerance with a view to assess the maximum workload performance with in period of 8-12 minutes. An experience doctor or an exercise physiologist will supervise the test. Continuous monitoring of 12 leads ECG and blood pressure will be performed. Data will be recorded continuously and stored digitally for analysis later on by an experienced exercise physiologist. Central pulse wave morphology and velocity will be determined pre and post exercise (+5minutes) by Sphygmocor device.

c) Holter Recording

4- 7 days Holter recordings will be obtained to determine recurrence of AF along with its burden. Briefly, a 3-lead electrocardiogram is recorded continuously by way of five electrodes positioned on the upper torso. Upon completion of the recording period, data will be imported into MediLog Darwin analysis software and automatically analysed by using R-wave detection.

E. STUDY INTERVENTIONS IN ADDITION TO STANDARD OF CARE IN AF PATIENTS

a) Non-invasive central blood pressure assessment

Non-invasive evaluation of central blood pressure indices and carotid-femoral PWV analysis will be performed as per IMPULSE-AF validation study protocol (CALHN Ethics and Research Committee Approval: R2010712, HREC Reference: HREC/16/RAH/269)

Non-invasive central blood pressure assessment will be performed at baseline, and at follow-up using the SphygmoCor applanation tonometry device (Fig 1). Central blood pressure indices, including central systolic, diastolic and pulse pressures with augmentation index will be recorded. Carotid-femoral pulse wave velocity (PWV) will be performed by applanation tonometry as per IMPULSE AF study protocol. The test is painless and typically takes10-15 minutes. In control patients, central blood pressure measurement will be performed as a single clinical assessment during their first visit after randomisation.

b) Atrial Fibrillation Severity Scale (AFSS)

Atrial Fibrillation Severity Scale (AFSS) will be used to quantify AF symptomatic burden. The AFSS is a validated scale with range of 3.25 [single

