Retinal photographs will be acquired from AF patients at baseline and during their follow up appointments yearly. Retinal vascular calibre will be measured from photographs using a validated computer program[22]. Retinal arteriolar and retinal venular calibre equivalents will be measured, and correlated with changes in central or peripheral blood pressures[22]. The acquisition of retinal image takes couple of minutes and it is a painless procedure that does not require any specific preparation.

[figure not shown]

Fig. 1. Sphygmocor applanation tonometry device (http://atcormedical.com/sphygmocor.html)

F. OUTCOMES OF THE STUDY

Primary outcomes to be evaluated include:

Association and Impact of central blood pressure control on AF outcomes (recurrence and AF burden).

Secondary Outcomes:

- Prevalence of central high blood pressure and aortic stiffness in AF patients with normal brachial BP.
- Association of brachial and central blood pressure indices including aortic stiffness to end organ insult and electro-anatomical remodeling of atria in AF patients.
- Correlating central blood pressure treatment target goals to proportionate decrease in events [Nephropathy (20% increase in ACR or 15-20% drop in estimated glomerular filtration rate (eGFR)), Left ventricular hypertrophy (LVH)/mass, LV diastolic dysfunction. Left atrial area and conduit vascular remodeling.
- Defining exaggerated BP response to exercise and postural change in our AF cohort and relating it with outcomes.
- > Number of anti-HTN required to achieve BP targets.
- Adverse events secondary to anti-HTN drugs including symptomatic postural BP drop of >20mmHg, acute kidney injury and electrolytes imbalance requiring hospitalization.

G. ETHICAL CONSIDERATIONS

Clinical Equipoise

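### The secondary end-organ outcome is worded as a correlation with central blood pressure target goals, so it does not state the randomised comparison that aim 2 needs

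*Protocol*

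**What the plan says.** - **Outcome (Section F, Secondary Outcomes).** The bullet reads "Correlating central blood pressure treatment target goals to proportionate decrease in events". It then lists nephropathy (defined by change in albumin-creatinine ratio or eGFR), LV hypertrophy or mass, LV diastolic dysfunction, left atrial area and conduit vascular remodelling. It does not mention the arms.
- **Objective (Specific Aims, aim 2).** "Prognostic impact of central high BP treatment to pre-defined targets as per age (Table-1) on clinical outcomes in AF patients".
- **Source of the goals (Section D, Table 1).** The table is captioned "Central Arterial Systolic Pressure (CASP) normal range as per age" and has one row per decade of age. No other central target values are given.
- **Who has the goals (Section D).** Only one arm is treated to Table 1: "Intervention group will have their anti-hypertensive therapy titrated as per central blood pressure targets (Table-1"). Controls are managed on brachial pressure under existing guidelines and have no central goal.
- **Other influences on treatment (Section D).** "The risk profiling will include age of the participants, aortic pulse wave velocity, baseline BP, degree of HTN induced end organ injury", together with exercise response and pressure indices. These inform treatment decisions but come with no target values.
- **Central pressure in controls (Section E(a)).** "In control patients, central blood pressure measurement will be performed as a single clinical assessment during their first visit after randomisation".

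**The concern.** Aim 2 is a treatment-effect question, and the trial randomises patients on that contrast. The bullet covering most of the end-organ measures instead describes a correlation with the goals. Nothing elsewhere supplies the missing comparison. The between-group difference in the sample size paragraph concerns AF recurrence. The other end-organ bullet in Section F is also an association. In the Statistical Analysis paragraph, the t-test is tied to agreement between peripheral and central recordings, and Pearson's method to blood pressure indices.

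At stake is what the trial could report on these outcomes. An author following the bullet would report a relation found inside the treated arm. Such a relation can appear when treatment does nothing and can be absent when treatment works. The unbiased comparison, for which most of the data are already scheduled, would not be a stated outcome.

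**Working it through.** The protocol gives no numerical figure for this outcome, so there is none to reproduce. The check takes each reading of the bullet in turn.

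**1. Goals read as the Table-1 value**

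Inputs from Table 1: age-band midpoints x = 25, 35, 45, 55, 65, 75, 85; average central systolic pressure y = 101, 105, 108, 112, 115, 119, 122 mmHg. Minimum and maximum are y − 11 and y + 11 in every row, so the choice of column does not change the correlation.

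- Sxx = 2 × (30² + 20² + 10²) = 2800
- Sxy = −30×101 − 20×105 − 10×108 + 10×115 + 20×119 + 30×122 = 980
- Syy = 87704 − 782²/7 = 343.4
- Slope = 980/2800 = 0.35 mmHg per year
- r = 980/√(2800 × 343.4) = 0.999

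For individual patients the goal is a step function of age, so the correlation is slightly lower: 0.985 if ages are uniform over 20-80, and 0.95 if they have mean 62 and SD 10. Both age distributions are assumptions.

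Within the intervention arm, write logit P(event) = a + b(age − 60) + log(OR), where OR is the treatment odds ratio. Every patient in that arm is treated, so log(OR) is absorbed into the intercept. A treatment effect that is equal at all ages therefore does not create a goal-event correlation; the age slope b does. A large simulation with assumed a = −1 gave:

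| Age slope b (log-odds per year, assumed) | Treatment OR | Goal-event correlation, uniform ages | Goal-event correlation, mean 62, SD 10 |
|---|---|---|---|
| 0 | 1, 0.5 or 0.25 | about 0 | about 0 |
| 0.04 | 1 (no effect) | 0.26 | 0.16 |
| 0.04 | 0.5 | 0.21 | 0.13 |
| 0.04 | 0.25 | 0.16 | 0.10 |

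The correlation is present with no treatment effect once events rise with age, and absent with a strong effect when they do not. The table shows the mechanism only; it does not estimate what would happen in this trial.

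**2. Goals read as attainment**

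Attainment is observed after randomisation. Section D says treatment decisions will weigh pulse wave velocity, baseline pressure and existing end-organ injury. These plausibly affect both whether a patient reaches the goal and whether end-organ measures worsen, and the last belongs to the same domain as the outcome. A relation between attainment and events is therefore confounded. It is also a within-arm quantity, because only intervention patients are titrated to a central goal. Follow-up central readings in controls would not turn it into a randomised contrast.

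**3. Is a between-arm comparison feasible?**

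| Assessment | Intervention (Table 2) | Control (Table 3) | Common visits |
|---|---|---|---|
| Echo | 0, 9, 18-20 months | 0, 11-13, 18-20 months | 0 and 18-20 |
| Serum and urine analysis | 0, 9, 18-20 months | 0, 11-13, 18-20 months | 0 and 18-20 |
| Renal function tests at follow-up | 3, 6, 9, 12, 15, 18-20 months | no 3-monthly tests; serum at 11-13 and 18-20 | 18-20 |

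Counting any renal event over follow-up would give the intervention arm six occasions to record a fall in eGFR, against at most two in controls. A comparison restricted to common visits avoids that imbalance.

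**4. Conduit vascular measures**

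Section E(a) gives controls a single central assessment. Section D(b), within the assessments offered to all participants, has SphygmoCor pulse wave morphology and velocity taken before and after exercise. Table 3 schedules control exercise tests at 0, 11-13 and 18-20 months. The two statements do not agree on whether controls have follow-up vascular data.

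**The case against.** The strongest reply is that the bullet is an item in an outcome list and not an analysis. The Statistical Analysis paragraph attaches no method to it, and a statistical analysis plan may exist. Elsewhere the protocol speaks of target goals as something to be achieved, so correlating the mmHg value itself is the less plausible reading. A decrease also needs a comparator, and with aim 2 and the randomised design the authors may well have meant a comparison with control.

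Much of this stands. A reader might infer that the protocol commits the trial to testing an age trend. It does not: that follows only from the literal reading, and no test is specified. A reader might also quote a false-positive rate. Simulations with an assumed 40% event risk and assumed event odds ratios of 1.3 to 1.75 per decade of age give significant goal-event correlations in about 20% to 64% of null trials at 90 treated patients. But the 40% is the planning figure for AF recurrence, the age gradients are invented, and several of the outcomes are continuous, so these are not error rates for this protocol. The inference that a spurious result would favour the trial is likewise speculation. Nor is it settled that controls lack follow-up vascular data.

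What does not stand is the suggestion that only detail is missing. The outcome is stated, and it is stated as a correlation. An analysis plan that implemented it as written would not estimate the effect in aim 2. The intended comparison has to be inferred, since no sentence commits to comparing the arms on these measures.

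**Conclusion.** The point holds in a limited form. The bullet does not match aim 2, and neither the goal-value reading nor the attainment reading uses the randomised comparison. The first largely tracks age; the second is a confounded post-randomisation variable defined for the intervention arm. This rests on Table 1 being the only source of central targets and on those targets applying to the intervention arm, both of which the protocol states.

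No size can be put on the consequence, because the protocol gives neither event rates nor age gradients for the end-organ outcomes. The stronger conclusions set out in the objection are not supported. The primary outcome and the sample size are unaffected. This is a secondary outcome that should be corrected, and doing so costs almost nothing.

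**What to change.** Replace the bullet in Section F with wording such as:

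*Difference between the randomised arms, by intention to treat, (a) in the proportion of patients with each renal event at 18-20 months relative to baseline, as a risk difference with 95% CI; and (b) in LV mass, LV diastolic indices and left atrial area at 18-20 months, adjusted for the baseline value. Only assessments at visits common to both arms (0 and 18-20 months) contribute.*

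Then:

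- **Conduit vascular measures.** Reconcile Section E(a) with Section D(b) and Table 3. Include these measures in the between-arm comparison only if controls have them at follow-up.
- **Goal attainment or achieved central pressure against events.** Keep as a labelled exploratory analysis, adjusted for age and baseline pressure, and without causal wording.
- **Renal data in controls.** Confirm that the 18-20 month serum sample yields eGFR, since Table 3 schedules serum analysis without naming renal function tests in that column.

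The cost is one rewritten bullet and a routine analysis. Echo, serum and urine collection is already scheduled in both arms at 0 and 18-20 months. The only possible extra cost is any vascular follow-up in controls that the reconciliation shows is wanted but not planned.

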Demographics and cardiovascular (CV) risk profiling	CPI and PWV including lying and standing CBP	CPI and PWV including lying and standing CBP	CPI and PWV including lying and standing CBP	CPI and PWV including lying and standing CBP	CPI and PWV including lying and standing CBP	CPI and PWV including lyin and standing CBP		
*CPI and PWV including lying and standing CBP (Sphygmocor)	AFSS, RFTS	AFSS, RFTS	AFSS, RFTs	AFSS, RFTs	AFSS, RFTs	AFSS, RFTs		
Echo, EST, Holter 4-7 days, AFSS, Retinal examination, Serum and urinary analysis.	Holter 4-7 days	Holter 4-7 days	Echo, EST, Holter 4-7 days, Serum and urine analysis	Holter 4-7 days, Retinal examination	Holter 4-7 days	Echo, EST, Holter 4-7 day Retinal examination, Serum and uri analysis		

Tables to illustrate follow up and intervention time lines for two groups

*Offer treatment as per central BP targets. (Table-1).

Additional electro-anatomical mapping to estimate scar burden along with CMRI will be offered to patients listed for AF ablation. The CMR will be repeated after 12 months to assess AAD in a year as per IMPULSE AF protocol (CALHN Ethics and Research Committee Approval R2010712, HREC Reference: HREC/16/RAH/269)

Table-3. Follow up and Investigations time line for Control Group (AFSS= AF symptom scale, BBP= Brachial blood pressure, CBP= central blood pressure, CPI= central pressure indices, EST= exercise stress test, PWV= pulse wave velocity, RFTs= Renal function test)							
0 months	6months	11-13 months	18-20 months				
Demographics and cardiovascular risk profiling	BBP treatment targets as per current guidelines	BBP treatment targets as per current guidelines	BBP treatment targets as per current guidelines				
CPI, PWV (Sphygmocor) Brachial blood pressure (BBP) including lying and standing assessment, Retinal examination	Review for standard CV risk factor modification including AF and anti HTN treatment	Review for standard CV risk factor modification including AF and anti HTN treatment	Review for standard CV risk factor modification including AF and anti HTN treatment				

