episode with minimal symptoms lasting for minutes] to 30 [continuous highly symptomatic episode lasting for 48 hours]. The scale also includes AF event frequency (scored 1-10), duration (scored 1.25-10) and global episode severity (scored 1-10). In addition, the AFSS assesses symptom severity via an associated symptom-specific continuous subscale (range, 0 [no symptoms] to 35 [severe symptoms]).

c) Serum and Urine Analysis

Venous blood samples (10ml) will be drawn from an antecubital vein after 10 minutes of supine rest and within five minutes following peak exercise to analyse atrial natriuretic peptide, serum markers of endothelial function (asymmetric dimethyl arginine, nitrate/nitrite), coagulation inflammation and fibrosis (C-reactive protein(CRP), tissue growth factor beta (TGF-B) and tumour necrosis factor (TNF)). Samples will be collected in appropriate tubes, centrifuged and plasma stored at -80°c. A preferably early morning urine sample will be collected to quantify albumin creatinine ratio (ACR).

- *d)* Recording of additional Electrophysiological (EP) parameters during AF ablation: Some of the study AF patients will be scheduled for pulmonary vein isolation (AF ablation) on clinical grounds at the Royal Adelaide Hospital. Conventionally, electro-anatomic mapping of the left atrium is performed by using the 3D mapping system during AF ablation. The following additional electrophysiological parameters will be recorded from the ablation catheter for these patients to characterise electro-anatomical atrial remodelling: effective refractory period, linear catheter conduction time, conduction velocity, proportion of fractionated electrograms, and bipolar voltage from the electroanatomic mapping system. This will add an extra 15mins to the procedure time without any additional requirements.
- *Non-contrast cardiac MRI (CMR) assessment of aortic distensibility.* In sub-group of 20-30 patients, scheduled for PVI (AF ablation) a non-contrast CMR will be performed to assess aortic distensibility (AAD) as per IMPULSE AF study Protocol (CALHN Ethics and Research Committee Approval: R2010712, HREC Reference: HREC/16/RAH/269). A repeat CMR will be performed to appraise (AAD) in a year's time.

f) Retinal photography and analysis

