The study is a low risk, single blinded randomised trial to evaluate the impact and treatment of central high blood pressure on AF and CV outcomes. Central high blood pressure will be estimated by validated cuff based device (Sphygmocor) non-invasively. Vascular remodelling secondary to HTN, leads to aortic stiffness, which is a modifiable risk factor. At present, it is known that various anti-hypertensive agents can have significantly different effects on central aortic pressures despite similar brachial blood pressure valuation [23]. Agents such as inhibitors of the renin-angiotensin system and amlodipine could be started in individuals with increased aortic stiffness. As such, the investigators regarding the conduct of this study identify no specific ethical concerns.

Informed Consent

All patient participants will undergo a formal process of informed consent prior to study participation. Patients will be blinded with regard to their randomised group and will be treated for peripheral or central high blood pressure accordingly.

Drugs

No additional pharmaceuticals will be administered for the study protocol, with the exception of anti-HTN to achieve treatment target goals re central or brachial blood pressure. Side effects of anti HTN medication will be recorded by conventional clinical approach of reviewing the symptoms, documentation of postural drop in BP and monitoring of renal function tests during follow up or as required clinically.

Specific Safety Consideration

No significant increase in radiation dose is anticipated for the acquisition of electrophysiological data for the study because we are going to use 3D mapping to position the catheters in atria. The non-invasive assessment of blood pressure is not associated with any known risk. Retinal photography does not require any mydriatics.

H. ANALYSIS AND REPORTING OF RESULTS

Sample size calculation

Assuming the recurrence risk is 40% for AF in control, we estimate 90 patients in each group would give us 80% power to detect the 20% difference between groups at 5% significance level. Anticipating dropout rate of 28% over the course of the study, we would like to recruit 126 patients in each group.

Statistical Analysis

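### The secondary nephropathy event has an ACR limb with no floor or confirmation, which many stable patients could meet by chance, and an eGFR limb written as a band instead of a cut-off

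*Protocol*

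**What the plan says.** Section F (Secondary Outcomes) sets the aim of "Correlating central blood pressure treatment target goals to proportionate decrease in events" and lists nephropathy first among those events. It is defined as "Nephropathy (20% increase in ACR or 15-20% drop in estimated glomerular filtration rate (eGFR"), and either limb is enough. The section gives no minimum ACR, no abnormal category and no confirmatory sample.

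Section E(c) describes the urine test: "A preferably early morning urine sample will be collected to quantify albumin creatinine ratio (ACR"). That is one spot sample per occasion, with the time of day only preferred.

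The schedules are as follows:

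- **Intervention arm (Table 2).** Urine is taken at baseline, at 9 months ("Echo, EST, Holter 4-7 days, Serum and urine analysis") and at 18-20 months. Renal function tests appear at every three-monthly follow-up, six in all.
- **Control arm (Table 3).** Serum and urine are taken at baseline, 11-13 months and 18-20 months. There is no renal function test entry. The serum list in Section E(c) does not name creatinine. Section D(a) lists renal function for everyone at baseline only. Section G adds monitoring during follow-up or when clinically required, without fixing a number.

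**The concern.** A purely relative rule on a variable test scores measurement noise as disease. To illustrate, a patient whose ACR goes from 0.5 to 0.6 mg/mmol has risen by exactly 20% and is recorded as having nephropathy, however low both values are.

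The eGFR limb has a different fault. A range is not a threshold. A 17% fall counts if the cut is 15% and does not if it is 20%. Read literally, a 30% fall lies outside the range.

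The outcome is meant to show fewer events with central pressure control. If many events in both arms are false, a true renal difference shrinks and may be missed. If one arm is also tested more often, the remaining false eGFR events do not fall equally on the two arms.

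**Working it through.** **Plan's own figure.** The protocol states no expected nephropathy rate and no variability for ACR or eGFR, so there is nothing to reproduce. The CVs below are assumptions, shown as ranges.

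**Model.** A patient has no true change, and within-person variation is log-normal with s = sqrt(ln(1 + CV²)). The log ratio of one follow-up to baseline then has standard deviation s·√2.

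**ACR limb**

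- One follow-up: P = 1 − Φ(ln 1.2 / (s·√2)).
- Either of two follow-ups: the two ratios share a baseline, so they correlate at 0.5; P comes from the bivariate normal.
- Both follow-ups: twice the one-follow-up figure minus the either figure.

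Worked case, CV 30%: s = 0.2936; 0.1823/(0.2936 × 1.4142) = 0.439; P = 33.0%. Either of two: 48.0%. Both: 2 × 33.0 − 48.0 = 18.0%.

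| ACR CV (assumed) | One follow-up | Either of two | Both |
|---|---|---|---|
| 10% | 10% | 16% | 3% |
| 20% | 26% | 39% | 13% |
| 30% | 33% | 48% | 18% |
| 40% | 37% | 53% | 21% |
| 50% | 39% | 55% | 23% |

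**eGFR limb, one follow-up:** P = Φ(ln(1 − d) / (s·√2)), with d = 0.15 or 0.20.

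| eGFR CV (assumed) | Crosses −15% | Crosses −20% |
|---|---|---|
| 5% | 1.1% | 0.1% |
| 7% | 5.0% | 1.2% |
| 8% | 7.5% | 2.4% |

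The ACR limb dominates. With ACR CV 30%, eGFR CV 7% and a 15% cut, adding the eGFR limb raises the one-follow-up rate only from 33% to 36%.

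**Unequal eGFR testing.** This was simulated with no true change, a 15% cut and an event at any visit. Control is given its two serum visits, on the assumption that creatinine is measured there; intervention is given its six renal function tests.

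| eGFR CV | Control, 2 tests | Intervention, 6 tests |
|---|---|---|
| 5% | 2% | 5% |
| 7% | 9% | 19% |
| 10% | 20% | 38% |

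**Dilution.** Suppose every true event is counted and a fraction f of the rest is falsely counted in both arms. The observed rate is p + (1 − p)f, so the observed difference is the true difference times (1 − f).

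- f = 26-39% (one follow-up) leaves 74-61% of the true difference.
- f = 39-55% (either of two) leaves 61-45%.

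Illustration with assumed true rates of 20% and 5%, and the 90 per arm from Section H (normal approximation, two-sided 5%): power is about 87% with clean measurement. At f = 39% the rates become 0.20 + 0.80 × 0.39 = 51.2% and 0.05 + 0.95 × 0.39 = 42.1%, a difference of 9.2 points, and power is about 23%.

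**The case against.** The best reply is that this is one element of one secondary outcome, that the variability figures are not the protocol's, and that which visit counts, or whether a repeat is needed, may be settled in an analysis plan not shown here. The first two parts stand: the outcome is secondary, and every percentage is conditional on an assumed CV. The third stands in part. A counting rule could be set later, but the definition already fixed has no ACR floor and a band for eGFR, and one follow-up alone gives 26-39% at CVs of 20-50%.

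Three stronger readings are tempting, and the documents do not support them:

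- **About half of stable patients would be events.** This needs an ACR CV of about 30% or more and a rule that either visit counts. The protocol states neither. In this model a single comparison always stays below 50%.
- **Both limbs lie within ordinary test variation.** That fits the ACR limb. At CVs of 5-8% few stable patients cross either eGFR cut at one test.
- **Antihypertensive drugs would move the two limbs in opposite directions, or be scored as kidney damage.** Section G says only that "Agents such as inhibitors of the renin-angiotensin system and amlodipine could be started in individuals with increased aortic stiffness". The protocol gives no drug effect on ACR or eGFR. Each limb counts only worsening, so a fall in ACR could not cancel a fall in eGFR. The adverse-event item, "acute kidney injury and electrolytes imbalance requiring hospitalization", is separate from an outpatient eGFR change if the hospitalization condition covers both conditions it names.

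**Conclusion.** The point holds in conditional form. From the text alone, the ACR limb has no absolute floor and no confirmation, and the eGFR limb is not a usable threshold. Under log-normal variation with an assumed ACR CV of 20-50%, 26-39% of unchanged patients meet the ACR limb at one follow-up and 39-55% at either of two; at a CV of 10%, 10% and 16%. The choice between the ends of the eGFR band matters: 1-8% of stable patients cross the lower cut and 0.1-2% the higher one at a single test, for an assumed CV of 5-8%.

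The unequal renal testing in Tables 2 and 3 adds a bias against the intervention arm if an eGFR event at any visit counts. Equal testing would not cure the ACR rule or the band. The change should be made, but it does not bear on the primary outcome or its sample size.

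**What to change.** In Section F, replace the combined event with two separate comparisons at 18-20 months: the between-arm difference in log ACR adjusted for baseline log ACR, and the between-arm difference in eGFR adjusted for baseline eGFR. State that the serum analysis at that visit includes creatinine in both arms.

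If an event is kept as a supporting outcome:

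- Give eGFR one threshold, worded as a fall of at least that size.
- Require the ACR rise to reach an abnormal level and to be present at both scheduled follow-up urines. The repeat alone brings false ACR events down to about 13-23% at CVs of 20-50%; the floor can only lower this further.
- Count only the visits common to both arms, at about 9-13 and 18-20 months. Asking for two consecutive scheduled tests would not do. At a 15% cut and CV 7%, six tests would still give 3.9% false events against 1.2% with two.
- Report ACR and eGFR separately.

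The cost is a wording change and confirmation that creatinine is part of the control arm's serum analysis. The urine samples are already scheduled and no visit is added. The downside is that fewer events will be counted.
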